same to research personnel. If obtaining informed consent is not feasible and a legally authorized representative is not reasonably available, the informed consent will be sent via trackable means. The letter will be sent via trackable means and documentation of the addressee and date of mailing and the delivery confirmation with will be kept in the study folder. The subject or their LAR will return the consent using a study provided postage paid envelope. If a signed consent document is not obtained, ~~we don't receive any signed~~ no research activities will be performed nor data will be extracted from the medical record, beyond 36 hours period covered by the Waivers of Consent and HIPAA. Samples and data acquired under those Waivers will be retained.

Whole Blood Transfusion Sites: Busy, Level 1 trauma centers from within the LITES Network will be selected based upon the ability to enroll patients with the proposed inclusion and exclusion criteria who have already implemented or are in the direct process of implementing an urgent release whole blood resuscitation protocol and are able to perform all necessary requirements for the planned prospective cohort study proposed. Those sites with the capabilities to deliver at least 4 units of WB will be selected for participation with preference given to ≥ 6 units urgent release WB capabilities. WB sites will be selected based upon the ability to enroll 33% of patients for the overall cohort study. As WB resuscitation becomes increasingly more widely adopted, there exists the potential to include additional WB sites from within the network as respective institutional practice changes over the 4 year time point of the study. Similarly, there exists the potential to incorporate additional trauma sites into the LITES network based upon their abilities to enroll poly-trauma patients in hemorrhagic shock and the utilization of WB resuscitation. As different trauma sites may utilize differing WB products with different titer levels, matching processes, and leukocyte reducing capabilities, these WB characteristics will be documented for all sites and for all WB units and respective patients enrolled.

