Sample Tracking, Management and Storage: After sample obtainment, processing and storage, samples will initially be batched sent to the University of Pittsburgh biological sample repository where it will be tracked, managed and stored until the necessary translational or mechanistic measurement are performed. The CCC and DCC have a long track record of coordinating such processes.

Power Analysis: The prospective cohort study will utilize time to 4 hour mortality for its primary outcome to power the study. Based upon the 6 LITES Network sites admission history that will be utilized and their respective volume of hemorrhagic shock patients meeting inclusion and exclusion criteria and a 3.5 year enrollment time period, we plan to initiate sampling on 1,050 patients over the enrollment time period of the study. With an 85% consent rate which is an estimate based upon prior studies of similar nature, we will consent for participation 892 patients for the study. With an estimate baseline rate of 4 hour mortality of 11.1 % derived from the PROPPR study, there will be 90% power to detect a hazard ratio of 1.9.

Calculations are based on the primary aim of the study based on the following assumptions:

- Type I error rate of 0.05
- Two-sided alternative hypothesis

Linking Investigations in Trauma and Emergency Services

Task Order 2: Shock, Whole blood and Assessment of TBI (SWAT)

- 6 sites will be involved, three whole blood and three component sites
- Each site will enroll 175 participants in 3.5 years of enrollment, of which, 85% will be eligible for the study (149)
- The calculations are based on Cox proportional hazard model
- A 4 hour event rate in the control (non-whole blood) group of 0.111

The power calculations for these secondary aims are presented below. When reporting the results of the analyses, caution will need to be taken with respect to the interpretation of the findings since they are secondary in nature.

The secondary outcomes in Aim 1B include binary outcome, continuous outcomes, and time to event outcomes. For the binary outcomes, the odds ratio that can be detected is presented in Table 1. For the continuous outcome, the effect size that can be detected is 0.13. Finally, for the time to event outcomes, the hazard ratio that can be detected over a range of event rates in the control group is also presented in Table 1.

Event Rate	.1	.2	.3	.4	.5	.6
Odds Ratio	1.76	1.56	1.49	1.46	1.46	1.48
Hazard Rate	2.69	1.70	.37	.30	.27	.30

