- For Aim 1C, a nonparametric analysis of variance will be used to compare the distribution of the GOS-E between the two groups. An effect size of 0.17 could be detected.
- For aim 2A, a nonparametric analysis of variance will be used to compare the distribution of the GOS-E between the two groups. An effect size of 0.28 could be detected.
- For aim 2B, a nonparametric correlation coefficient will be used to assess the association between GOS-E and the area under the systolic blood pressure curve. For each, a 95% confidence interval with a width of 0.19 can be estimated.
- For all secondary analyses, the type I error rate was set to 0.05, with a two-sided alternative hypothesis, and 90% power. For the Aim 1, the sample size will be 1,190. For Aim 2, the sample size will be limited to those with a traumatic brain injury. For the purposes of this study, this is expected to be 35% or a total of 417 participants.

Analyses

AIM#1: The analysis will begin by describing the baseline demographic and clinical characteristics of the overall population and then stratified by whole blood usage. The characteristics will be

Linking Investigations in Trauma and Emergency Services

Task Order 2: Shock, Whole blood and Assessment of TBI (SWAT)

compared among those who receive and who do not receive whole blood. For discrete variables, proportions will be generated and a chi-square test will be used to test for differences between the proportions. For continuous characteristics, means (medians) and standard deviations (interquartile ranges) will be calculated and t-tests (Wilcoxon) will be used to compare the means (distributions) among those who receive and do not receive whole blood.

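### Site selection aims for whole-blood sites to supply 33% of the cohort, but the power assumptions imply 50% and the printed detectable odds ratios match equal groups

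*Combined protocol and SAP*

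**What the plan says.** **Site selection.** The section Whole Blood Transfusion Sites states: "WB sites will be selected based upon the ability to enroll 33% of patients for the overall cohort study". It adds that further whole-blood sites may join as practice changes, but gives no revised share.

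**Power assumptions.** The bullets in Power Analysis state: "6 sites will be involved, three whole blood and three component sites", and "Each site will enroll 175 participants in 3.5 years of enrollment, of which, 85% will be eligible for the study (149"). The text above them says "we plan to initiate sampling on 1,050 patients over the enrollment time period of the study" and "we will consent for participation 892 patients for the study".

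**Secondary outcomes.** "For the binary outcomes, the odds ratio that can be detected is presented in Table 1". The row reads 1.76, 1.56, 1.49, 1.46, 1.46, 1.48 at event rates .1 to .6. The basis follows the table: "For all secondary analyses, the type I error rate was set to 0.05, with a two-sided alternative hypothesis, and 90% power", and "For the Aim 1, the sample size will be 1,190".

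**Comparison.** Under Analyses, AIM#1 and Hypothesis#1A, patients are compared by whether they received whole blood, not by type of site. No number of whole-blood patients is printed anywhere.

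**The concern.** One section points to about one third of the cohort coming from whole-blood sites; another builds the power statement on one half. For a fixed total, unequal groups give less information, so a detectable effect worked out for equal groups is too favourable for a one-third share. The share also fixes how many whole-blood patients the study can expect, which is the scarce group in this design. A reader of the power table cannot tell that it depends on a split that site selection does not ask for.

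**Working it through.** **1. Shares implied by the text**

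- Power Analysis: 3 × 175 = 525 at whole-blood sites and 3 × 175 = 525 at component sites, total 1,050. After the 85%: 3 × 149 = 447 in each. Share 50%.
- Whole Blood Transfusion Sites: 33% of 1,050 = 347 (350 if 33% means one third). Share 33%.

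**2. Reproducing the printed odds ratios**

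Inputs from Power Analysis: N = 1,190, two-sided 0.05, 90% power, control rates p₁ = .1 to .6. The test is not named; I assume the usual two-proportion z-test with pooled variance under the null and no continuity correction.

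- p₂ = OR·p₁ / (1 − p₁ + OR·p₁)
- power = Φ[(|p₂ − p₁| − 1.96·s₀) / s₁]
- s₀ = √[p̄(1 − p̄)(1/n₁ + 1/n₂)], s₁ = √[p₁(1 − p₁)/n₁ + p₂(1 − p₂)/n₂]

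Worked case, p₁ = .1 and OR = 1.76: p₂ = 0.1636, difference 0.0636.

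- 595:595: s₀ = 0.01961, s₁ = 0.01952; (0.06357 − 0.03844)/0.01952 = 1.29; power 90%.
- One third whole blood (793:397): s₀ = 0.02007, s₁ = 0.02141; (0.06357 − 0.03933)/0.02141 = 1.13; power 87%.

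Solving for the odds ratio at 90% power:

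| Control rate | .1 | .2 | .3 | .4 | .5 | .6 |
|---|---|---|---|---|---|---|
| Printed | 1.76 | 1.56 | 1.49 | 1.46 | 1.46 | 1.48 |
| N = 1,190, 1:1 | 1.76 | 1.56 | 1.49 | 1.46 | 1.46 | 1.48 |
| N = 1,190, one third | 1.81 | 1.59 | 1.52 | 1.49 | 1.49 | 1.52 |
| Power for printed OR, one third | 87% | 87% | 87% | 86% | 86% | 86% |

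All six printed values match equal groups. Taking the share as exactly 33% changes a few entries by 0.01.

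**3. Does anything else give the printed row?**

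- N = 892, 1:1, 80% power gives the same six values. That is again an equal split, but not the stated N or power.
- N = 1,050, 33% share, 80% power with a continuity correction gives 1.76, 1.56, 1.49, 1.46, 1.46, 1.49. It misses the last value and contradicts the stated N and power.
- The hazard-ratio row did not reproduce under the Schoenfeld formula with either split at 892, 1,050 or 1,190, so it is not used here.

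**4. Primary outcome**

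Schoenfeld: power = Φ(|ln HR|·√[d·a(1 − a)] − 1.96), where a is the whole-blood share and d the deaths; N = 892, control rate 0.111.

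- Benefit, HR = 1/1.9: whole-blood rate 1 − 0.889^(1/1.9) = 0.060. At 1:1, d = 446 × (0.111 + 0.060) = 76 and power is 80%. At one third, d = 84 and power is 79%.
- HR = 1.9 taken as harm: 97% at 1:1, 92% at one third.
- 0.111 applied to everyone (d = 892 × 0.111 = 99), which comes close to the stated 90%: 89% at 1:1, 85% at 33%.

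**5. Size against the separate sample-size conflict**

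At N = 892, 1:1 and 90% power the odds ratios are 1.90, 1.66, 1.58, 1.55, 1.55, 1.58. At the .1 rate, the change of N alone moves 1.76 to 1.90 (0.14); the change of split alone moves 1.76 to 1.81 (0.05).

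**The case against.** The best defence is that 33% is a capability used to choose sites, not an allocation. Read as a minimum, it is compatible with three whole-blood sites reaching half the cohort, and the protocol expects whole-blood sites to be hard to find at first and possibly added later. This stands as a possible reading. The text does not say that it is a minimum, though, and the power bullets do not mention the 33%, so the two shares still need reconciling. A per-site reading is also conceivable, but the sentence refers to the overall cohort.

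The second defence is size: 0.03 to 0.05 on the odds ratio and 3 to 4 points of power, for secondary outcomes that the plan already says to interpret with caution. That also stands, and it limits the weight of the point.

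Some stronger readings are not supported:

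- A reader might infer that the stated precision cannot be reached at any sample size with a one-third share. It can: about 1,310 to 1,360 patients restore 90% power for the printed values.
- A reader might infer that the table proves two groups of 595. It supports equal groups; 446 per group at 80% power gives the same row.
- A reader might infer that a safety estimate in whole-blood patients is undermined. The plan specifies no whole-blood-only safety analysis and claims no precision for one.
- A reader might infer that the analysed split will be 1:2. The comparison is by receipt, and no receipt rate is given for either type of site.

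**Conclusion.** The inconsistency is real and the wording does not resolve it. On the stated basis of 1,190 patients and 90% power, the odds ratios belong to equal groups. If 33% is the planned share, they carry 86–87% power and the detectable values rise to 1.81, 1.59, 1.52, 1.49, 1.49 and 1.52. About 175 fewer of the 1,050 sampled patients would come from whole-blood sites (350 against 525).

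This does not threaten the primary analysis in the direction of Hypothesis #1A: power for a hazard ratio of 1/1.9 is 80% at equal groups and 79% at one third. That 80% lies below the stated 90% for reasons other than the split.

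The result rests on a pooled two-proportion test, on no allowance for clustering or propensity adjustment, and on treating site share as exposure share. The last is a simplification, and the documents give nothing with which to improve on it. The conflict between 1,190 and 892 patients has a larger effect and needs its own correction; settling it would leave the share unresolved. The point should be corrected because the plan relies on a stated power that the site-selection share, read as a target, does not deliver.

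**What to change.** - State one planned whole-blood share, in the same terms, under Whole Blood Transfusion Sites and in the Power Analysis assumptions, and say whether 33% is a target or a minimum.
- Define that share as the expected proportion of patients who receive whole blood, since that is what the analysis compares, and give the assumed receipt rate at each type of site.
- Restate the detectable effects and the expected number of whole-blood patients for that share, at the sample size actually planned. If 33% is a minimum, show the figures at 33% and at 50%.

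The cost is wording and one recomputed table, with no change to conduct. The figures become slightly less favourable if the share is below 50%.

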Hypothesis #1B: *Whole blood resuscitation will be associated with a lower incidence of 12 hour and 24 hour mortality, a lower incidence of death from exsanguination, incidence of MOF, nosocomial infection, improved transfusion ratios, lower overall blood transfusion requirements and shorter time to hemostasis as compared to those resuscitated with component therapy.*

Hypothesis #1C: *Whole blood resuscitation will be associated with an improved Glasgow Outcome Score-Extended at 6 months post injury as compared to those resuscitated with component therapy in patients with traumatic brain injury.*

Hypothesis #2A: *A nadir prehospital and acute phase resuscitation systolic blood pressure greater than or equal to 120 mmHg will be associated with improved traumatic brain injury outcomes at discharge and at 6 months.*

Linking Investigations in Trauma and Emergency Services

Task Order 2: Shock, Whole blood and Assessment of TBI (SWAT)

Hypothesis #2B: *The magnitude of the dose depth curve of systolic blood pressure during the prehospital and acute phase resuscitation will be associated with neurological outcome differences at discharge and at 6 months following traumatic brain injury.*

Research Design and Methods

Study Design: The LITES Network will perform a multicenter, prospective, observational cohort study over a 4 year period to determine the impact of whole blood resuscitation in trauma patients with hemorrhagic shock at risk of large volume resuscitation with and without TBI. Early whole blood resuscitation will be compared to standard component resuscitation. The study will also further characterize blood pressure and resuscitation endpoints in poly-trauma patients with traumatic brain injury. Six trauma sites with appropriate characteristics will be selected from network sites across the country. (Figure 2)

Figure 2

Study Setting: The study will be performed utilizing busy level I trauma centers from within the LITES Network located across the country, at sites where either whole blood has currently been incorporated into standard of care or where component blood transfusion is being utilized for patients in hemorrhagic shock at risk for large volume resuscitation. Due to the paucity of trauma centers who are currently utilizing whole blood for trauma patients as standard of care, the potential to incorporate additional sites may be required over time.

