Hypothesis#1A: For the primary outcome, the time to death will be generated for each participant. Kaplan-Meier curves will be generated for each treatment group and a log-rank test will be used to compare the distribution of the cumulative proportion. A hierarchical Cox-proportional hazards regression model will be used to control for the within-institution clustering. The hierarchical Cox-proportional hazards regression model will then be used to assess the independent impact of whole blood on time to death after controlling for the clustering effect and potential confounding effects of baseline characteristics. The model will include main effects for whole blood usage and a propensity score for receiving whole blood. The propensity score for the use of whole blood will be generated using a boosted logistic regression model. The dependent variable in the model will be the use of whole blood and the independent variables will be the baseline characteristics of the population. The Cox-proportional hazards model will be used to estimate the cumulative probability of death 4 hours.

Hypothesis#1B: The analytic approach for the secondary outcomes included in Hypothesis#1B will vary based on the type of outcome. For binary outcomes (e.g., 12 hour and 24 hour mortality, death from exsanguination, incidence of MOF, nosocomial infection), the same analytic approach that was carried out for Hypothesis 1a will be implemented.

For continuous outcomes (e.g., transfusion ratios, blood transfusion requirements) a two-sided t-test for correlated means will be used to compare the means between those receiving and not receiving whole blood. A hierarchical analysis of variance model will be used to control for the within-institution clustering. The model will be used to assess the independent impact of whole blood after controlling for the clustering effect and the potential confounding. The model will include main effects for whole blood usage and propensity for receiving whole blood.

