Interim Analysis: There will be two aspects of the interim analysis. First, for efficacy, the Lan and Demets approach will be utilized to conduct the interim efficacy analysis. This approach is preferable over other approaches because it is flexible to the number of interim analyses conducted during the course of the study. The Lan and DeMets approach requires the use of a spending function to allocate the type I error to the interim analysis. The O'Brien and Fleming spending function which minimizes the type I error allocated to the interim analysis, saving the vast majority for the primary analyses will be used. For the proposed interim analysis, assuming that 50% of the study will be completed, it is estimated that the type I error allocated to the interim analysis will be 0.005, leaving 0.048 of the type I error for the primary outcome analysis.

Linking Investigations in Trauma and Emergency Services

Task Order 2: Shock, Whole blood and Assessment of TBI (SWAT)

Time Line: The study will occur over a 4 year period with a 6 month start up period, an interim analysis at 2 years and a 3.5 year enrollment period.

Linking Investigations in Trauma and Emergency Services

Task Order 2: Shock, Whole blood and Assessment of TBI (SWAT)

BIBLIOGRAPHY

3. Hoyt DB. A clinical review of bleeding dilemmas in trauma. *Semin Hematol*. 2004;41(1 Suppl 1):40-43.

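### Whole-blood use may expand during the 3.5-year enrollment, but no outcome or propensity model names calendar time, so part of any mortality trend could be attributed to whole blood

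*Combined protocol and SAP*

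**What the plan says.** Three statements allow whole-blood exposure to change while patients are being enrolled.

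- Whole Blood Transfusion Sites expects wider adoption and says that "there exists the potential to include additional WB sites from within the network as respective institutional practice changes over the 4 year time point".
- The same section admits centers "who have already implemented or are in the direct process of implementing an urgent release whole blood resuscitation protocol", so use can begin or ramp up within an enrolled site.
- Study Setting adds that "the potential to incorporate additional sites may be required over time".

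The Time Line gives "an interim analysis at 2 years and a 3.5 year enrollment period". The four years mentioned under Whole Blood Transfusion Sites are the length of the whole study.

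The planned starting point is concurrent. Power Analysis states "6 sites will be involved, three whole blood and three component sites". Whole Blood Transfusion Sites gives a different share: "WB sites will be selected based upon the ability to enroll 33% of patients for the overall cohort study".

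On the primary analysis, Hypothesis#1A specifies a hierarchical Cox model: "The model will include main effects for whole blood usage and a propensity score for receiving whole blood". The propensity score comes from a boosted logistic model on baseline characteristics that are not listed. The secondary Aim 1 models have the same structure. In Aim 2, the Hypothesis#2A propensity model names site and whole-blood use, but not time. No section says how a site that changes practice is analyzed, and no sensitivity analysis addresses a time trend. Data Collection includes time of injury (Prehospital Data) and arrival time (ED Data).

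**The concern.** The comparison is not randomized, so anything that moves with both exposure and mortality is a confounder. Calendar time is a candidate that the plan itself points to: it expects whole-blood practice to grow, and its Background describes trauma resuscitation as having changed over the preceding decade.

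Nothing written into the model removes a time trend. The Cox time axis is time to death for each patient, so the baseline hazard does not absorb calendar date. A site random effect absorbs stable differences between hospitals, not drift within them. When a site switches during the study, the random effect moves weight onto that site's before-and-after contrast, which is where a trend does most damage. Exposure is defined by the patient's receipt of whole blood, so a site that is still introducing its program supplies early component patients and later whole-blood patients.

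At stake is the primary 4-hour mortality estimate and, through the shared model structure, the Aim 1 secondary estimates.

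**Working it through.** **Inputs from the documents.** N = 892, control 4-hour mortality 0.111, six sites of equal size split 3:3, two-sided alpha 0.05 (Power Analysis); 3.5 years of enrollment (Time Line).

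**Assumptions not in the documents.** True hazard ratio (HR) 1.00; even accrual; a log-linear trend in the 4-hour hazard, the same at every site, with end-to-start ratio r = 0.9, 0.8, 0.7 or 1.25; one or two component sites convert at mid-enrollment; no other confounding, so the propensity score is left out.

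**Step 1: the plan's own benchmark.** Events = 892 × 0.111 = 99.0. Power = Φ(√(99.0 × 0.25) × ln 1.9 − 1.96) = Φ(3.193 − 1.96) = 0.89, in line with the stated 90% for an HR of 1.9 (1/1.9 = 0.53 if protective). This only sets a scale.

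**Step 2: the trend by halves.** Under a log-linear trend, mean hazard in the second half divided by that in the first is s = √r.

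**Step 3: constant whole-blood share.** At 3:3 throughout, the apparent HR is [(3 + 3s)/6] / [(3 + 3s)/6] = 1.00 for every r. At a constant 33% share it is [(2 + 2s)/4] / [(4 + 4s)/8] = 1.00. A common trend alone causes no bias.

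**Step 4: changing share, no site terms.** Count site-halves.

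- One site converts (3:3, then 4:2): HR = [(3 + 4s)/7] / [(3 + 2s)/5].
- Two sites convert (3:3, then 5:1): HR = [(3 + 5s)/8] / [(3 + s)/4].

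For r = 0.8 and two sites: s = 0.894, (3 + 4.472)/8 = 0.934, (3 + 0.894)/4 = 0.974, ratio 0.959.

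**Step 5: within-site contrast only.** With fixed site terms under this scenario, only converting sites carry information, and the apparent HR is s itself.

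| r | One converts, no site terms | Two convert, no site terms | Within-site only |
|---|---|---|---|
| 0.9 | 0.991 | 0.981 | 0.949 |
| 0.8 | 0.981 | 0.959 | 0.894 |
| 0.7 | 0.970 | 0.936 | 0.837 |
| 1.25 | 1.019 | 1.043 | 1.118 |

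A hierarchical model lies between the no-site-terms and within-site columns, nearer the latter as between-site variance grows. Starting instead from a 33% share (2:4, then 4:2), HR = (2 + 4s)/(4 + 2s) = 0.983, 0.964 and 0.942 for the three falling trends. To two decimals these match the two-site column, so the choice between the two stated shares does not matter here.

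**Step 6: add calendar time.** With the trend in the model, the HR returns to 1.00 in every scenario. Standard errors of the log HR at r = 0.8, taking the starting cumulative hazard as −ln(1 − 0.111) = 0.118:

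| Scenario | Without time | With time | Increase |
|---|---|---|---|
| One converts, no site terms | 0.209 | 0.211 | 1% |
| Two convert, no site terms | 0.217 | 0.228 | 5% |
| One converts, fixed site terms | 0.506 | 0.541 | 7% |
| Two convert, fixed site terms | 0.358 | 0.413 | 15% |

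**The case against.** The best defense is that the planned design has concurrent whole-blood and component sites, and expansion is a possibility with no number or date attached. Added whole-blood sites may be network centers not yet enrolled, and nothing under Component Transfusion Sites describes one switching. This stands. A reader might infer that component sites are scheduled to convert, or that any secular trend will be credited to whole blood. The documents support neither: Step 3 shows no bias while the share is constant.

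A reader might also infer that the bias always favors whole blood. It does so only if mortality falls while the share rises; the documents give no mortality trend, and the r = 1.25 row goes the other way.

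Nor is enrollment date ruled out. The baseline characteristics are unlisted, and Hypothesis#2A counts site among them, so the category is not confined to clinical variables. Timing data are collected. It would also be too strong to say that only converting sites offer a within-site contrast: a whole-blood site may hold as few as 4 units, and any of its patients given components alone would be concurrent controls.

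Finally, the bias is small beside an HR of 1.9. With two conversions and no site terms, the nominal 5% type I error becomes 5.1% to about 6% over the trends shown. In the within-site case at r = 0.8 the bias is ln 0.894 = −0.112 against a standard error of 0.358 to 0.506, under one third of a standard error.

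These points limit the size and certainty of the problem. They do not remove the gap: the plan foresees a changing exposure and names no term that would handle it.

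**Conclusion.** The point holds as a conditional one. The plan allows whole-blood use to expand during enrollment and names no calendar-time term in any outcome or propensity model. If the whole-blood share and mortality both change over time, part of the trend is attributed to whole blood, in whichever direction mortality moves.

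Under the assumed trends, with two of three component sites converting at mid-enrollment, a null effect would appear as an HR between 0.98 and 0.84 when hazard falls by 10% to 30%, depending on the trend and on how far the estimate rests on within-site contrasts. A 25% rise would give 1.04 to 1.12. One conversion without site terms gives at most a 3% distortion over these trends. The trends, the number of conversions and their timing are all assumptions. The illustration also leaves out the propensity score, which would help only if it captured calendar time or the case-mix changes behind the trend.

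The change is worth making because it protects the primary estimate of a non-randomized comparison from a confounder that the plan itself foresees, at low cost.

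**What to change.** - Name enrollment date, as a spline or as enrollment periods, in the Aim 1 propensity model and as a covariate in the primary and secondary hierarchical models.
- Derive it from the injury or arrival time already collected. Recruitment and Consent says that identifiers are stripped at data entry, so confirm that the date, or at least the enrollment period, is kept in the analysis file.
- State how a site that changes practice during enrollment is analyzed, and report a time-adjusted within-site estimate for any such site.
- Settle this before outcomes are compared by exposure.

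No new data collection is needed if dates are retained. In the illustration at r = 0.8, the main-model standard error rises by about 1% (one conversion) to 5% (two). The within-site estimate costs more, 7% to 15%, and is imprecise in any case, so it is best reported as supportive.
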